10.3.3 Analysis of Safety

Analysis of safety data will be performed for all subjects in the Safety Population.

Adverse events will be coded using Medical Dictionary for Regulatory Activities (MedDRA) and classified by system organ class and preferred terms. Adverse events will be summarized by total number of TEAEs, number of subjects reporting TEAEs, ocular TEAEs (affecting the study eye and/or the non-study eye and/or both eyes, when appropriate), non-ocular TEAEs, SAEs, serious and unexpected suspected adverse reactions (SUSARs), discontinuing study drug due to an AE, by relationship to study drug and/or ocular surgical procedure, and by severity.

The IOP data for both eyes will be summarized at screening, Visit 6 (POD22)/Early Termination (Withdrawal) visit and change from screening. The observed IOP data and change-from-baseline (POD1) for the study eye will be summarized at each post-surgery visit.

The data for slit lamp biomicroscopy examination endpoints will be summarized at each visit. The summary of change-from-baseline at each post-surgery visit will be presented for the study eye.

Dilated indirect ophthalmoscopic examination findings for the study and non-study eye will be summarized at screening and Visit 6 (POD22)/Early Termination (Withdrawal).

Visual Acuity data will be summarized at each visit. The summary of change-from-baseline at each post-surgery visit will be presented for the study eye.

10.3.4 Analysis of Corneal Endothelial Cell Parameters

The corneal endothelial cell parameter data (corneal endothelial cell density [cell/mm²], percent hexagonality and coefficient of variation) from the Endothelial Cell Sub-study will be summarized at each assessment visit. The mean change from baseline (Visit 1/Screening) for each treatment group and the mean difference with 95% confidence interval between treatment groups will be calculated at Visit 7 (POD85) for the three parameters, as appropriate. The percent change from baseline at Visit 7 (POD85) for corneal endothelial cell density will also be summarized.

10.3.5 Interim Analysis

No interim analyses are planned for this study.

10.4 SAMPLE SIZE ESTIMATION

The assumption for the sample size determination was estimated using the Package Inserts of Durezol®, Lotemax® and Inveltys® and results from the APP13007 Phase 2 study (CPN-201). The sample size for ACC count primary efficacy endpoint is based on the assumption of 26% of subjects in the APP13007 group with ACC Count = 0 at POD8 and maintained through POD15 and 12% of subjects in the matching vehicle placebo group. The two-group chi-square test, with a two-sided significance level of 5% and 92% power, requires 175 subjects per treatment group to detect the difference between APP13007 and placebo.

The same sample size using the assumption of 57% of subjects with Ocular Pain Grade = 0 at POD4 and maintained through POD15 in APP13007 group and 38% of subjects in placebo group will provide 95% power to detect the treatment difference.

With an estimated 5% dropout rate, this study will randomize approximately 185 subjects per treatment group for a total of approximately 370 subjects.

In the Endothelial Cell Sub-study, a sample size of 80 subjects per treatment group is considered adequate to evaluate the corneal endothelial cell parameters between treatment groups. With a 10% dropout rate, the Sub-study will enroll approximately 88 subjects per treatment group for a total of approximately 176 subjects to be randomized for the Endothelial Cell Sub-study.

10.5 LEVEL OF SIGNIFICANCE

Unless otherwise specified, all statistical tests will be two-sided and the statistical significance will be tested at the 5% level.

The primary efficacy endpoints will be evaluated using the fixed sequence testing described in [Section 10.3.2.1](#).

10.6 PROCEDURE FOR ACCOUNTING FOR MISSING, UNUSED, OR SPURIOUS DATA

If more than 5% of data points are missing at POD15 in any treatment group, a tipping point analysis will be performed to assess the sensitivity of the primary efficacy results to the distribution of the allocation of treatment success and failure to the missing data points. Other missing data imputations will be detailed in the SAP.

10.7 PROCEDURE FOR REPORTING DEVIATIONS FROM THE STATISTICAL PLAN

Any deviations from the SAP will be described and a justification given in the final clinical study report.

10.8 SUBJECTS TO BE INCLUDED IN THE ANALYSIS

All efficacy analyses will be performed using the ITT population. In addition, the analysis of the primary efficacy endpoints will be performed using the PP population as a supportive analysis. AEs and other safety endpoints will be analyzed using the Safety Population.

11.0 SUPPORTING DOCUMENTATION AND OPERATIONAL CONSIDERATIONS

11.1 REGULATORY, ETHICAL AND LEGAL OBLIGATIONS

11.1.1 Declaration of Helsinki

The Principal Investigator will ensure that this study is conducted in accordance with the most recent revision of the Declaration of Helsinki.

11.1.2 Good Clinical Practice

The Study will be conducted according to the study protocol and to Standard Operating Procedures (SOPs) that meet the guidelines provided by the International Conference on Harmonisation (ICH) for Good Clinical Practice in clinical studies and applicable regulatory requirements.

11.1.3 Institutional Review Boards

This protocol and the informed consent form must be approved by an appropriately constituted and qualified IRB and the approvals made available to the Sponsor or designee prior to the start of enrollment into the study. Materials used to recruit subjects or supplied to subjects for the study will be approved by the appropriate IRB and the approvals made available to the Sponsor or designee prior to their use. In addition, the APP13007 Investigator's Brochure will be

submitted to the IRB. Written IRB approval must adequately identify the protocol and informed consent form. Copies of all approved materials, all correspondence with the IRB, and written approval from the IRB must be made available to the Sponsor (or designated Study Monitor).

Any modification of study procedures or amendments to the protocol must be approved by the IRB and submitted to FDA prior to implementation. In the event that a modification or amendment is considered by the Investigator to be immediately necessary to ensure subject safety, the Investigator will promptly notify his or her IRB, the Study Medical Monitor, and the CRO for Study Management and Monitoring who will then notify the Sponsor.

Investigators will report all SAEs reported at their site to their IRB, as appropriate.

11.1.4 Informed Consent Process

Written informed consent will be obtained from each participant prior to any study-related procedures being performed (prior to or on the Screening visit). A copy of the signed and dated informed consent document will be given to each subject. The original signed and dated informed consent document must be maintained in the study files at the investigative site and be available for the CRO for Study Management and Monitoring and the Sponsor or designee(s) to review.

Each informed consent will contain Investigator contact information with a telephone number the subject or the subject's authorized representative can call 24 hours a day and 7 days a week if they have medical concerns.

11.1.5 Subject Confidentiality and Disclosure

Study personnel will have access to a subject's protected health information (PHI). This information may be obtained by the Sponsor, which includes any persons or companies that are working with, working for, or owned by the Sponsor. PHI may be given to the U.S. FDA Department of Health and Human Services agencies, other governmental agencies in the U.S., governmental agencies in other countries, and governmental agencies to which certain diseases (reportable diseases) must be reported.

11.2 MONITORING AND AUDITING STUDY DOCUMENTATION

The Investigator(s)/institution(s) will permit trial-related monitoring, audits, IRB review, and regulatory inspection(s) by providing direct access to source data and documents (such as tests performed as a requirement for participation in the study and other medical records) to the Study Monitor or the Sponsor or its designee.

11.2.1 Clinical Monitoring

Before an investigational site can enter a subject into the study, a representative of the Sponsor or its designee such as the CRO for Study Management and Monitoring [REDACTED] [REDACTED] and its Study Monitor will perform pre-study site evaluation at each of the investigational study sites in person or remotely to:

- Determine the adequacy of the facilities
- Discuss with the Investigator(s) and other personnel their responsibilities about protocol adherence, and the responsibilities of the Sponsor or its designated Study Monitor and representatives. This will be documented in a Clinical Study Agreement between the Sponsor (Formosa Pharmaceuticals, Inc.) and the Investigator.
- Confirm qualified staff are trained on the protocol, study processes and systems.
- Confirm all supplies and study product are onsite and stored accordingly.
- Collect any outstanding essential documents.

During the study, a monitor from the Sponsor or its designated CRO for Study Management and Monitoring [REDACTED] and its Study Monitor or representative will have regular contacts with the investigational site, for the following:

- Provide information and support to the Investigator(s).
- Confirm that facilities remain acceptable.
- Confirm that the investigational team is adhering to the protocol, that data are being accurately recorded in the eCRFs, and that study treatment accountability checks are being performed.
- Perform source data verification. This includes a comparison of the data in the eCRFs with the subject's medical records at the investigational site, and other records relevant to the study. This will require direct access to all original records for each subject (e.g. clinic charts or electronic records).
- Record and report any protocol deviations not previously sent to the Sponsor and the IRB.
- Confirm the site has adequate supplies and study drugs.
- Confirm AEs and SAEs have been properly documented in eCRFs and confirm that any and all SAEs have been forwarded to the Sponsor via the CRO for Study Management and Monitoring and those SAEs that met criteria for reporting have been forwarded to the IRB.

The Study Monitor and other representatives at the CRO for Study Management and Monitoring will be available between visits if the Investigator(s) or other staff needs information or advice.

11.2.2 Auditing of Sites and Study Documentation

Quality control and quality assurance may be performed before, during, and after the study by the Sponsor or Sponsor's designee, such as the CRO for Study Management and Monitoring and its Study Monitors. Regulatory authorities in certain countries reserve the right to audit study sites following submission of data in regulatory applications. The Investigator may be given due notice of any intended audit by a regulatory body. By signing this protocol and the FDA Form 1572, the Investigator acknowledges that these inspection procedures may take place and agrees to provide access to the required subject records and other study documentation. Furthermore, the Investigator agrees to inform the Sponsor via the CRO for Study Management and Monitoring immediately of any known or suspected inspection by authorities. If the Investigator does not comply with the protocol, GCP, or regulations, the Sponsor reserves the right to disqualify the Investigator and/or site from the current or future protocols.

11.3 DATA HANDLING AND RECORD KEEPING

All procedures for the handling and analysis of data will be conducted using GCP and will meet ICH guidelines and US FDA regulations for the handling and analysis of data for clinical trials.

11.3.1 Data Collection and Management Responsibilities

After data have been entered into the study database, a system of computerized data validation checks will be implemented and applied to the database. Query reports pertaining to data omissions and discrepancies will be forwarded to the Investigator and Study Monitor(s) from the CRO for Study Management and Monitoring for resolution. The study database will be updated in accordance with the resolved query reports. All changes to the study database will be documented.

11.3.2 Study Records Retention

The study center will retain all records related to the study in accordance with local and ICH GCP guidelines.

11.4 PROTOCOL DEVIATIONS

Monitoring will be conducted to verify compliance. Instances of minor, major and critical deviations that occur at investigative sites will be documented and communicated to the Sponsor and documented at the investigative site and recorded in the eCRF. Any noted protocol deviations meeting the IRB reporting requirements will be reported to the IRB.

11.5 PUBLICATION AND DATA SHARING POLICY

The Institutions and Investigators participating in this trial shall have no right to publish or present the results of this study without the prior written consent of the Sponsor.

APPENDIX A: CONTINGENCY PLANS RELATED TO THE COVID-19 PANDEMIC

In March 2020 the FDA issued the Guidance: “Conduct of Clinical Trials of Medical Products during COVID-19 Pandemic”.

Based on the stated goal in this FDA Guidance, the following plans may be implemented:

1. When a clinical site plans to or has to close operations and visits cannot be scheduled per protocol:

- If possible, schedule an Early Termination/Withdrawal visit before the clinical site closes.
 - Ask subject to stop the study drug, if before Visit 5 (POD15).
 - Collected study drug and dosing diary.
 - Conduct the Visit 6 (POD22) assessments.
- A Protocol Deviation is documented as “Early Termination/Withdrawal visit performed because the study site closed for operations prior to completion of the study visits due to COVID-19 infection-control requirements”.

2. When a subject cannot or does not want to return for an in-person visit:

- The clinical site coordinator contacts the subject by telephone (or alternative method of communication) and asks the subject to stop the study drug, if before Visit 5 (POD15), and collects AE and concomitant medication information.
 - The available information is entered in the Early Termination/Withdrawal section of the eCRF.
 - If before Visit 5 (POD15), the study coordinator requests the subject to send the study drug bottle and dosing diary to the study coordinator at the clinical site.
- The Investigator withdraws the subject from the study and considers alternative methods of assessing the subject.
- A Protocol Deviation is documented as “Subject withdrawn early (Early Termination) and the assessments for Visits X, Y and Z were not performed because the subject could not or did not want to return for an in-person visit due to COVID-19 infection-control requirements”.

**APPENDIX B: GUIDANCE THAT MAY BE USED FOR GRADING
THE SEVERITY OF A NUCLEAR, CORTICAL OR
POSTERIOR SUBCAPSULAR CATARACT IN THE
NON-STUDY EYE**

Location	Minimal	Mild	Moderate	Severe
Nuclear	Minimal Changes in nuclear zone	In the nuclear zone, the anterior and posterior embryonal nuclei are distinctly more opalescent (more visible) than normally seen, but the central clear zone is still easily distinguishable in its entirety	The nuclear zone is more uniformly opaque and the central clear zone between the anterior and posterior nuclei is not clearly visible. The posterior part of the zone is often more opaque.	The nuclear zone is densely opaque with more or less uniform nuclear opacity extending to the edge of the nuclear zone; nuclear features are only partially visible, if at all.
Cortical	Cataract involves $< \frac{1}{8}$ of the circumference	Cataract involves $\frac{1}{8}$, but less than $\frac{1}{4}$, of the circumference.	Cataract involves $\frac{1}{4}$, but less than $\frac{1}{2}$, of the circumference.	Cataract involves $\geq \frac{1}{2}$ of the circumference.
Posterior subcapsular	< 1 mm	≥ 1 mm, but < 2 mm	≥ 2 mm, but < 3 mm	≥ 3 mm

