6.4.3 Handling Dropouts or Missing Data

6.4.3.1 Imputation of Missing Efficacy Data

The missing data handling rule for the study eye will be applied for the efficacy endpoints.

Missing data from subjects who discontinue the study before POD15 assessments without taking rescue medication:

For subjects who prematurely discontinue the study without taking rescue medication, the LOCF approach will be used to impute the missing data. The last observation will be the last assessment value after the first dose of study drug and up to two days following the last dose of study drug.

Missing data from subjects who discontinue the study before POD15 assessments and take rescue medication before POD15 assessments:

For both categorical and continuous secondary efficacy endpoints of ACC grade, ocular pain grade and ACF grade, subjects who take rescue medication before POD15 assessments and prematurely discontinue the study, the LOCF approach will be used to impute the missing data. The last observation will be the last assessment value after the first dose of study drug and prior to starting rescue medication.

Intermittent missing data:

The likelihood of having intermittent missing data is low. For subjects with intermittent missing data for efficacy endpoints, the LOCF approach will be applied to impute the missing data, i.e., using the data collected from the most recent prior visit after the first dose of study drug.

If no data can be carried forward (i.e., missing assessments at POD 4 visit or no available post-baseline assessments), missing data will be treated as missing for the continuous endpoints and will be considered as 'Non-responder' for the categorical endpoints.

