6.4.4 Handling of Dropouts Due to the COVID-19 Pandemic

The [protocol Appendix A](#) describes the Early Termination/Withdrawal procedures that may be implemented because of the COVID-19 pandemic. Subjects who discontinue the study due to COVID-19 will follow the imputation rules described in [Section 6.4.3.1](#) to impute the missing efficacy data.

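### Where applied, Appendix A item 2 withdraws a subject from the whole study over one COVID-related missed visit, losing POD85, POD22 and late POD15 data that could still be collected.

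*Protocol*

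**What the plan says.** Protocol Appendix A lists plans that sites may put in place during the pandemic. Item 2 is triggered "When a subject cannot or does not want to return for an in-person visit". The site telephones the subject, asks them to stop study drug if POD15 has not been reached, collects AE and medication information, and enters it in the Early Termination section of the eCRF. Then: "The Investigator withdraws the subject from the study and considers alternative methods of assessing the subject". No alternative method is named. The model deviation text refers to several visits not performed.

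Elsewhere the protocol retains subjects who go off study drug. Sections 6.2.12 and 9.4.2 keep rescued subjects to POD22, or to POD85 in the Sub-study. Section 9.5.2 does the same for subjects whose study drug is stopped for persistent IOP elevation.

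The SAP treats dropout and a single missed visit separately. On dropout, Section 6.4.4 says: "Subjects who discontinue the study due to COVID-19 will follow the imputation rules", pointing to Section 6.4.3.1. On single missed visits, Section 6.4.3.1 says: "For subjects with intermittent missing data for efficacy endpoints, the LOCF approach will be applied to impute the missing data". Section 6.3.5 (Table 3) accepts a scheduled POD15 visit after Study Day 17 if the subject completed 14 days of dosing and was not rescued. The same section excludes efficacy assessments more than two days after the last dose when fewer than 14 days were dosed. Section 11 allows no imputation of safety data, which include the endothelial cell parameters.

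**The concern.** The trigger is one visit and the consequence is the end of study participation. A brief isolation has no bearing on whether a later visit can take place, yet item 2 gives no route back. A subject declared a treatment failure is followed to POD85, while a subject who was merely quarantined is not. The SAP's rule for intermittent missing data would seldom apply to a COVID-related miss, because item 2 turns the miss into a dropout.

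What is at stake is avoidable missing data. The POD85 measurement is the visit named in the Sub-study endpoint and cannot be replaced once lost. For POD15, an obtainable observation gives way to a carried-forward one, so a subject with zero cells at POD8 would count as an ACC responder on a single observed visit.

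**Working it through.** **1. The plan's own figures.** Protocol 10.4: "The two-group chi-square test, with a two-sided significance level of 5% and 92% power, requires 175 subjects per treatment group", with rates of 26% and 12%. Using n = [z(0.975)·√(2·p̄·q̄) + z(0.92)·√(p1q1 + p2q2)]² / (p1 − p2)² and p̄ = 0.19:
- n = (1.960 × 0.5548 + 1.405 × 0.5459)² / 0.14² ≈ 175.5, or 176 rounded up (stated 175).
- Power at 175 per arm is 91.9% for ACC (stated 92%) and 94.8% for pain at 57% against 38% (stated 95%).
- Main Study: 175 / 0.95 = 184.2, so 185 (stated 185). Sub-study: 80 × 1.10 = 88 (stated 88); 80 / 0.90 gives 89.

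The stated figures reproduce.

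**2. What each miss costs, and what retention alone would recover.**

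| Only visit missed | Later visits lost under item 2 (POD85: Sub-study only) | Recovered by retention alone |
|---|---|---|
| POD4 | POD8, POD15, POD22, POD85 | POD22 and POD85; POD8 and POD15 for the ACC endpoint in the SAP 10.1.4 analysis |
| POD8 | POD15, POD22, POD85 | POD22 and POD85; POD15 as observed data |
| POD15, after 14 days of dosing | a late POD15 visit, POD22, POD85 | all of them, with POD15 back in the primary analysis through Table 3 |
| POD22 | POD85 | POD85, due 85 − 22 = 63 days later |

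In the first two rows item 2 also stops study drug. POD8 then ordinarily falls more than two days after the last dose, and POD15 always does, so SAP 6.3.5 keeps them out of the primary analysis even if the subject attends.

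SAP 10.1.4 uses all data collected up to POD15. I read that as overriding the two-day limit, although the SAP does not say so. It scores a subject who lacks POD8 or POD15 as an ACC Non-responder, and one who lacks POD4, POD8 or POD15 as a pain Non-responder. The only 10.1.4 result that retention can change is therefore ACC after a missed POD4. After a missed POD8, the later POD15 value enters that dataset but cannot change either outcome.

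**3. How many subjects.** The documents give no miss rate. Assume each visit is missed independently with probability m, and that item 2 is applied at the first miss. Then POD15 is missing in 1 − (1 − m)³ and POD85 in 1 − (1 − m)⁵. Retention alone would save POD15 for the primary analysis only when POD15 is the first miss, (1 − m)²·m, assuming the late visit takes place. It would save POD85 in 1 − (1 − m)⁵ − m.

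| m | POD15 missing under item 2 | of which recoverable (per 185) | POD85 missing under item 2 | of which recoverable (per 88) |
|---|---|---|---|---|
| 1% | 3.0% | 1.0% (1.8) | 4.9% | 3.9% (3.4) |
| 2% | 5.9% | 1.9% (3.6) | 9.6% | 7.6% (6.7) |
| 3% | 8.7% | 2.8% (5.2) | 14.1% | 11.1% (9.8) |
| 5% | 14.3% | 4.5% (8.3) | 22.6% | 17.6% (15.5) |

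At m of about 2%, item 2 alone roughly uses up the 5% and 10% dropout allowances. It would also take missing POD15 data past the 5% level at which Protocol 10.6 calls for a tipping-point analysis.

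**4. Effect on precision.** Take 185 per arm and extra withdrawal c beyond the planned 5%. Withdrawn subjects are either dropped from the analysis or counted as non-responders, with each rate multiplied by 0.95 − c.

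| c | ACC power: dropped / non-responder | Pain power: dropped / non-responder |
|---|---|---|
| 0 | 92.0% / 91.7% | 94.9% / 94.0% |
| 5% | 90.6% / 89.9% | 93.8% / 91.7% |
| 10% | 89.0% / 87.8% | 92.5% / 88.9% |

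Sub-study subjects evaluable at POD85 number 88 × (0.90 − c): 79.2, 74.8 and 70.4 per arm. Relative to 80, √(80/n) makes the confidence interval about 0.5%, 3% and 7% wider.

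**The case against.** The strongest reply is about cause. A reader might infer that the withdrawal sentence is what removes POD8 and POD15 from the primary analysis, so that a missed POD4 costs three primary-endpoint visits. The documents do not support this. The ACC endpoint uses only POD8 and POD15. For pain, a missed POD4 with nothing to carry forward is a Non-responder under SAP 6.4.3.1 whatever follows. After a POD4 or POD8 miss, the instruction to stop study drug together with SAP 6.3.5 excludes later visits even for a retained subject. This part of the reply stands in full.

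It can also be said that:
- The plans are optional, and the trigger could be read as inability to attend any further visit; the multi-visit deviation text fits that reading. This stands as a limit. However, item 2 is the only plan offered for such a subject, and the text does not settle its scope.
- Analysis windows are wider than visit windows, so a short delay can be absorbed. This is true, but only for a subject still in the study.
- Alternative assessment is to be considered. None is named, and Protocol 7.3.4 requires specular microscopy images taken by certified site personnel.
- A subject may withdraw for any reason, and under Protocol 6.3 a request to stop study drug is itself an Early Termination. This stands for subjects who want to leave, but not for those who only cannot attend one visit.
- COVID dropouts have a stated imputation rule, and completer, observed-case and tipping-point analyses are planned. These help in judging the primary result but do not supply a missing POD85 measurement.

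**Conclusion.** The point holds within limits. Where a site applies item 2 to a single missed visit, three kinds of obtainable data are lost:
- POD85, and POD22 when the miss comes earlier;
- a late POD15 assessment after completed dosing;
- later observed data after a missed POD4 or POD8, which can alter the SAP 10.1.4 result only for ACC after a missed POD4.

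This is inconsistent with the retention of rescued subjects and of subjects who stop study drug for IOP. The POD85 loss is the most serious, because those data are not imputed and the endpoint is defined at that visit.

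It would go too far to conclude that the primary analysis is endangered. Even 5% extra withdrawal counted as failure leaves about 90% power for ACC and 92% for pain. The counts in the working rest on assumed, independent miss rates and on item 2 being applied at the first miss; the documents give neither. The change is worth making because it is cheap and the loss is avoidable.

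**What to change.** In Protocol Appendix A item 2, replace the withdrawal sentence with wording such as: *Record the visit as missed due to COVID-19. The subject remains in the study and attends the next scheduled visit that is possible, including a late POD15 visit and, for Sub-study subjects, Visit 7. The subject is withdrawn only if consent is withdrawn or no further visit is possible.*

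In SAP 6.4.4, add that a visit missed for COVID-19 by a subject who stays in the study is intermittent missing data under Section 6.4.3.1, and that a late POD15 visit meeting the Table 3 conditions is not missing.

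Separately, the sponsor should reconcile the study-drug instruction in item 2 with SAP 6.3.5 and 6.4.3.1, and say whether the two-day limit applies to the Section 10.1.4 analysis. No dosing rule is proposed here.

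The cost is a short protocol amendment, a few lines in the SAP, and some continued follow-up of subjects already scheduled for these visits. No procedure is added to the Schedule of Events.
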